9.9 COVID-19 vaccination and reporting

Where a deployed COVID-19 vaccine is suspected to be involved in the onset of a reported event, it should be recorded as a concomitant medication. A causal relationship between the vaccine and the event, including potential drug interactions should be assigned by the reporting investigator.

If a reported event is suspected to be due to a deployed COVID-19 vaccine alone, reporting investigators should ensure that standard Yellow Card reporting procedures are followed.

9.10 Notification of deaths

All deaths must be recorded within the eCRF. Where the death has a causative relationship with the IMP, it must also be reported as per section 9.2.

9.11 Reporting urgent safety measures

If any urgent safety measures are taken, the CI/Sponsor will phone the MHRA's Clinical Trials Unit on [name], ideally within 24 hours. This will be followed up no later than 3 days from the date the measures are taken, giving written notice to the MHRA (who will advise the format required) and the relevant REC of the measures taken and the circumstances giving rise to those measures. A substantial amendment must also be submitted to the MHRA.

9.12 Developmental Safety Update Reports

A Development Safety Update Report (DSUR) will be submitted once a year, or on request, to MHRA and REC until the trial is declared ended. The report will be submitted within 60 days of the anniversary of the issue of the Clinical Trials Authorisation for the trial. The DSUR will be prepared by the Sponsor in liaison with the Cl, and submitted by the Sponsor.

9.13 Pregnancy

Pregnancy is an exclusion criterion for the CLASP trial. If a participant with an undetected pregnancy is enrolled, or in the event of a pregnancy occurring up to Day 90, these are to be reported to the Sponsor using the pregnancy form (https://www.glasgowctu.org/Home/00-safety-reporting/).

Pregnancy is not in itself considered to be an adverse event, unless a negative or consequential outcome is recorded for the mother or child/foetus and this would be considered an SAE and must be reported as per SAE reporting procedure above.

Any pregnancy occurring in a female trial participant or female partner of a male trial participant who becomes pregnant while participating in the trial will be reported by the PI (or designee) to the Chief Investigator and the sponsor using the pregnancy form within two weeks of the PI first becoming aware of the pregnancy.

The pregnancy will be followed up for outcome, and the outcome reported to the Sponsor.

9.14 Overdose

An overdose will be defined as any dose administered above the trial specific parameters.

An overdose can be identified from the participant's medication charts and will be recorded in the protocol deviation log.

Any overdose must be reported to the trial centre with or without associated adverse events using the serious adverse event forms according to the timelines detailed above and local guidelines.

9.15 Responsibilities

This section details the responsibilities for reporting and reviewing safety information arising from the trial.

9.15.1 Data Centre

The Data Centre will:

- Provide an eCRF for central data collection of ARs and SAEs
- Coding of events using MedDRA, where required
- Provide the Sponsor PV Office with read-only access to relevant data and reporting facilities in the study database
- Provide reports, including safety information, to the independent oversight committees identified for the trial (TSC and IDMC).

9.15.2 Principal Investigator (PI)

- Checking for AEs and ARs when participants attend for treatment/follow-up
- Ensuring that AEs are recorded in line with the requirements of the protocol
- Using medical judgement in assigning seriousness, causality, and severity of events with reference to the trial protocol and Reference Safety Information

9.15.3 Chief Investigator (CI) and Co-CI

- Clinical oversight of the safety of patients participating in the trial, including an ongoing review of the risk/benefit.
- Using medical judgement to determine expectedness of SAEs.
- Preparing the clinical sections and final sign-off for the Development Safety Update Report (DSUR).

9.15.4 Sponsor

- Verification of data collection, AEs, SAEs, SARs and SUSARs according to the trial protocol
- Reporting safety information to the CI or delegate for the ongoing assessment of the risk/benefit
- Ensuring that SAE forms are completed fully and the data contained therein has been fully sense checked
- Reviewing the expectedness of SARs with reference to the RSI and reviewing all events related to the IMP or trial specific procedures
- Expedited reporting of SUSARs to the Competent Authority (MHRA in UK) and REC within required timelines
- Notifying Investigators of SUSARs that occur within the trial
- Checking for (annually) and notifying PIs of updates to the Reference Safety Information for the trial
- Preparing standard tables and other relevant information for the DSUR in collaboration with the CI and ensuring timely submission to the MHRA and REC.

9.15.5 Trial Steering Committee

In accordance with the TSC Charter, periodically reviewing recruitment and the overall progress of the trial and liaising with the IDMC and sponsor regarding safety issues.

9.15.6 Independent Data Monitoring Committee

In accordance with the IDMC Charter, periodically reviewing safety data in individual cases and to determine patterns and trends of events, or to identify safety issues, which would not be apparent on an individual case basis, reporting concerns to the TSC and sponsor.

10 STATISTICS AND DATA ANALYSIS

10.1 Sample size calculation

In our preliminary study of antibiotic classes [36] based on observational data we reported a common Odds Ratio (OR) of approximately 0.5 for those receiving macrolides. This observation was not a pre-specified hypothesis. We have applied the 'rule of thumb' to target an effect size that is half that observed in such circumstances. Working on the log OR scale, half the effect size can be back-transformed to our target OR of 0.7.

A sample size of 524 participants per group would give 90% power at a two-sided 5% significance level to detect a common OR of 0.7. This is based on analysis by ordinal logistic regression of the mRS at 90 days, assuming the distribution of 90 day mRS in the control arm to be 2:8:8:5:20:20:37 across mRS 0-6. We propose an adaptive (group sequential) design, with an interim analysis after 50% have provided primary outcome data. If the interim analysis z-statistic for the treatment effect is less than -3.09 (i.e. is in favour of clarithromycin at a one-sided p<0.001), then we shall stop the trial for efficacy. If the interim analysis statistic is greater than -0.5, we shall stop for futility. Otherwise, we shall complete the trial as planned, without adjustment of the final analysis p-value.

Simulations of this approach under alternative assumptions regarding the true common OR (N=10,000 simulated trials at ORs from 0.5 to 1.0) suggest that there is minimal loss of power, and no inflation of the Type I error rate (see Table 3 below). Under the null hypothesis of no treatment effect, the one-sided probability of a false positive result is 0.025, slightly lower than running the full trial (0.026), and there is a 69% probability that the trial will stop early for futility, leading to an expected total sample size of 685. If the true OR is equal to 0.7 (the target value

Version 1.0 – 12 December 2024

CLASP

for the sample size calculation), the power of the adaptive design is 88.3%, close to that achieved by running the full trial (89.8%), but with 25.5% chance of trial stopping early (21.7% for efficacy, 3.8% for futility), the expected sample size is 914. Should the true common OR be 0.5 (as observed in observational studies), the adaptive approach gave a positive result in all simulated trials, with 91.7% stopping early, leading to an expected sample size of 568 (Table 3).

| | Standard Approach | | Adaptive Approach | | | |
|--------------------------|-------------------|-------------------------|------------------------|-------------------------|--------------------------|--------------------------|
| Odds ratio | Sample Size | % Positive Trials | Mean Sample Size | % Positive Trials | % Stopped (Futile) | % Stopped (Effective) |
| 0.5 | 1048 | 100% | 568 | 100% | 0.0% | 91.7% |
| 0.6 | 1048 | 99.7% | 750 | 99.5% | 0.2% | 56.7% |
| 0.7 | 1048 | 89.8% | 914 | 88.3% | 3.8% | 21.7% |
| 0.8 | 1048 | 51.6% | 929 | 50.1% | 17.9% | 4.7% |
| 0.9 | 1048 | 15.5% | 819 | 14.8% | 43.1% | 0.7% |
| 1.0 (Null Hypothesis) | 1048 | 2.6% | 685 | 2.5% | 69.3% | 0.1% |

We feel that if the interim analysis is strongly in favour of clarithromycin, then there is no ethical reason to continue the trial, for example, to gain better information about treatment safety, since the trial treatment has a well-known safety profile. We believe that a trial of 524 patients with a strong treatment effect benefit will be sufficient to convince the majority of the medical community of the benefit of this treatment. Similarly, should the interim results appear futile, then there is no value in continuing to recruit additional patients.

We will recruit a total of up to 1166 participants to allow for up to 10% attrition.

10.2 Planned recruitment rate

In the 18-month internal pilot phase we aim to recruit 36 sites (80% of total sites) and 246 participants (21% of the total sample) at a rate of 0.55 participants/site/month during the first 6 months and 0.76 participants/site/month for the remaining 12 months.

Following the internal pilot phase if criteria are met for progression, the main recruitment phase (27 months) will recruit the remaining additional 9 sites (during the first 6 months) and 920 participants. The trial will aim for a recruitment rate of 0.7 participants/site/month for the additional 9 sites during set-up and 0.8 participants/site/month otherwise.

10.3 Statistical analysis plan

The interim analysis will be carried out according to a detailed Statistical Analysis Plan (SAP). This will be approved by both the TSC and IDMC. The SAP will be written by the trial statistician who will not have access to randomised treatment codes. The interim analysis program will be written and validated by statistical staff without access to randomised treatment codes. The program will be run (using live treatment codes) by a dedicated IDMC statistician who is not otherwise involved with the analysis for the study.

The final analyses will be carried out according to a detailed Statistical Analysis Plan, to be written and approved prior to database lock and unblinding of treatment allocations, according to GCTU SOPs.

10.3.1 Summary of baseline data and flow of participants

Baseline data to be collected is described in section 7.5. Numbers of participants completing each study assessment point will be reported. Numbers of participants completing or not completing the study will be reported, with reasons for non-completion.

10.3.2 Primary outcome analysis

The primary efficacy analysis will estimate the average treatment effect in those randomised to receive clarithromycin, according to the intention to treat principle.

Ordinal logistic regression will be used to analyse the primary outcome (mRS at 90 days). ORs, corresponding 95% confidence intervals and p-values will be reported.

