7.3 Randomisation

Patients will be randomised 1:1 to the following drug regimens:

- Intervention arm: Clarithromycin 500mg twice daily for 5 days total (route of administration will be determined by the local clinical team based on clinical condition and availability of route of administration in line with local IVOS policy) in addition to usual non-macrolide antibiotic treatment.
- Usual care: Local stroke unit usual non-macrolide antibiotic treatment.

A mixed minimisation/randomisation method designed to maintain balance with respect to baseline age (<80 v \geq 80 years), stroke severity (National Institutes of Health Stroke Scale (NIHSS) score <12 v \geq 12) and trial centre will be applied.

The randomisation list, the program that generated it and the random seed used will be stored in a secure network located within the Robertson Centre for Biostatistics (RCB), accessible only to those responsible for provision of the randomisation system.

CLASP

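### The primary OR and 95% CI carry no adjustment for the interim stopping rule: overall coverage is about 93.3–93.5% for true ORs of 0.70–0.85, and an efficacy stop reports an exaggerated OR

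*Protocol*

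**What the plan says.** Section 10.3.2 analyses the 90-day mRS by ordinal logistic regression and states that "ORs, corresponding 95% confidence intervals and p-values will be reported". It does not mention the interim rule.

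Sections 10.1 and 10.6 set one interim analysis once 524 participants have a 90-day mRS, half of 1048. A z below -3.09 stops the trial for efficacy and a z above -0.5 stops it for futility. If neither is met, section 10.1 says: "Otherwise, we shall complete the trial as planned, without adjustment of the final analysis p-value". Section 10.6 judges the final test at one-sided 0.025.

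The simulation table in 10.1 gives positive-trial rates, stopping rates and mean sample size, but nothing on the bias of the OR or the coverage of its interval. The same section expects an efficacy stop to be persuasive: "We believe that a trial of 524 patients with a strong treatment effect benefit will be sufficient to convince the majority".

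**The concern.** A stopping rule affects estimation as well as testing. A trial stops early for efficacy only when its estimate is already extreme, so the estimate reported at that stop tends to exaggerate the effect. A futility stop pulls the other way. An interval of estimate ± 1.96 SE, taken at whichever stage the trial ends, need not cover the true OR 95% of the time.

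The protocol has checked that the unadjusted p-value is safe for Type I error. It ties no adjustment to the OR and its interval, although the size of the effect is what clinicians would take from an early stop.

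**Working it through.** **Inputs**
- Section 10.1: "two-sided 5% significance level to detect a common OR of 0.7", "A sample size of 524 participants per group would give 90% power", and a control distribution given as "assuming the distribution of 90 day mRS in the control arm to be 2:8:8:5:20:20:37 across mRS 0-6".
- Section 7.3: "Patients will be randomised 1:1 to the following drug regimens".
- Section 10.6: look at 524 outcomes (information fraction 0.5), boundaries -3.09 and -0.5, final one-sided 0.025 (z < -1.96).

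**Step 1. Reproduce the plan's figures.** Proportional-odds sample size per arm:

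n = 6(1.960 + 1.282)² / [(ln 0.7)² (1 − Σp̄³)]

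Here p̄ is the mean of the control distribution and that distribution shifted by OR 0.7, so Σp̄³ = 0.0546. This gives n = 524.2, against 524 stated.

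The information on the log-OR scale at 1048 outcomes is V = 524 × 0.9454 / 6 = 82.6. At the interim it is 41.3, so the SE is 1/√41.3 = 0.156. A two-stage normal model with the stated boundaries then gives:

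| | Recomputed | Protocol |
|---|---|---|
| OR 0.7: fixed-design power | 90.0% | 89.8% |
| OR 0.7: adaptive power | 88.7% | 88.3% |
| OR 0.7: efficacy stop | 21.3% | 21.7% |
| OR 0.7: futility stop | 3.7% | 3.8% |
| OR 0.7: mean N | 917 | 914 |
| OR 1.0: positive trials | 2.4% | 2.5% |
| OR 1.0: futility stop | 69.2% | 69.3% |
| OR 1.0: mean N | 685 | 685 |

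The model matches the protocol's design closely.

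**Step 2. Overall coverage of the ordinary 95% CI** (estimate ± 1.96 SE at the stage where the trial ends):

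| True OR | 0.5 | 0.6 | 0.70 | 0.75 | 0.80 | 0.85 | 0.9 | 1.0 |
|---|---|---|---|---|---|---|---|---|
| Coverage | 95.9% | 95.0% | 93.3% | 93.4% | 93.3% | 93.5% | 94.6% | 95.1% |

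At OR 0.70 the figure is made up as follows:

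| Outcome | Probability | Coverage | Mean OR |
|---|---|---|---|
| Efficacy stop | 0.213 | 88.2% | 0.566 |
| Futility stop | 0.037 | 31.9% | 0.984 |
| Runs to completion | 0.751 | 97.7% | 0.715 |

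Coverage: 0.213 × 0.882 + 0.037 × 0.319 + 0.751 × 0.977 ≈ 0.933. The mean OR over all outcomes is 0.689. (OR means are geometric.)

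A separate simulation of 6,000 trials with actual proportional-odds fits gave 93.25% coverage (± 0.6 points) and a mean OR of 0.562 at an efficacy stop.

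**Step 3. The efficacy stop.** Crossing -3.09 at 524 outcomes needs an estimated OR below exp(−3.09 × 0.156) ≈ 0.62. Participants recruited but not yet at day 90 may be added to the reported analysis. The protocol gives no number for them. Assuming 130–200, at true OR 0.70 the mean reported OR becomes 0.59–0.60, and about 31–38% of efficacy stops end with an OR weaker than 0.62.

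**Step 4. What an adjustment does**
- A stage-wise-ordering interval has simulated coverage of 95.06% at OR 0.70.
- In a completed trial with final z = -3.24, the ordinary result 0.700 (0.564–0.869) becomes 0.704 (0.566–0.882). With final z = -1.96, 0.806 (0.650–1.000) becomes 0.802 (0.642–0.998).
- At an interim stop nothing precedes stage 1 in the ordering, so the stage-wise result equals the ordinary one. At z = -3.66 both give 0.566 (0.417–0.768).
- The bias-adjusted estimate at z = -3.66 is 0.582, a partial correction.

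**The case against.** **This belongs in the SAP.** Sections 10.3 and 10.9 defer to separate SAPs, which are not shown. The protocol does not call the interval ordinary, and its remark about no adjustment concerns the p-value. That is fair, and an SAP may already settle the matter. But the protocol itself names the OR and interval to be reported after a two-boundary rule and ties no adjustment to them, so the ordinary model interval is the natural reading.

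**The shortfall is small.** This stands. It is at most about 1.7 points, near zero at 0.6 and 1.0, and completed trials at OR 0.70 over-cover.

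Stronger readings that the protocol does not support:
- *The final test is compromised.* It is not: positive trials under the null are 2.4–2.5%.
- *The trial will report 0.57 when the truth is 0.70.* That is conditional on an efficacy stop at 524 outcomes. Over all outcomes the mean is 0.689, and at a true OR of 0.80 it is 0.81, slightly towards no effect.
- *A reported OR after an efficacy stop can never be weaker than 0.62.* This holds only for the 524-outcome analysis. Section 10.6 recommends ceasing recruitment, and section 7.10 ends the trial at the last Day 90 visit, so later outcomes may be added.
- *Stage-wise methods would cure the early-stop exaggeration.* They leave an interim-stop result unchanged.
- *The economic model inherits a biased OR.* Section 10.10 draws transition probabilities, resource use and utilities from the trial but does not name the common OR as an input.

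**Conclusion.** The point holds as a modest reporting matter. Near the effects the trial targets, an ordinary 95% CI covers about 93.3–93.5% of the time. After an efficacy stop at true OR 0.70 (about one trial in five), the mean OR is about 0.57 with 88% coverage, or about 0.59–0.60 with the assumed later outcomes included. At such a stop the interval is misplaced more than it is too narrow.

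This rests on four assumptions: the ordinary model interval is the one meant, proportional odds hold with the stated control distribution, the look falls at half the information, and the boundaries are followed. The minimisation covariates and the random centre effect were not modelled.

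**What to change.** In section 10.3.2, keep the ordinary OR and 95% CI and state that the trial will also report:
- a stage-wise-ordering 95% CI and median-unbiased OR for the -3.09/-0.5 boundaries. These restore 95% overall coverage when the boundaries are followed, though they change only completed trials, and only slightly;
- if the trial stops at the interim, a bias-adjusted OR, with a statement that an estimate from an early efficacy stop is likely to be exaggerated.

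State also whether participants already recruited when the trial stops enter the reported analysis. If they do, the adjusted methods must say how the added outcomes are handled. Fix all of this before the interim data are seen.

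The cost is a little more analysis work and, after an early efficacy stop, a slightly less favourable companion estimate (0.58 beside 0.566 at z = -3.66). Boundaries, sample size and the final test do not change.

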10.3.3 Secondary outcome analysis

Secondary outcome measures will be analysed using the following methods:

- Mortality at 90 days will be analysed using Cox proportional hazards models.
- Any urgent or unplanned re-admission to 90 days and recurrent stroke or vascular events will be analysed using logistic regression.
- Home time, stroke-related health status, health and social care resource use and caregiver burden will be analysed using general linear models.
- EQ-5D-5L at 90 days will be compared between treatment groups using a general linear model adjusted for the baseline EQ-5D-5L.
- Length of stay will be analysed using a negative binomial model.

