3.3.3 Exploratory outcomes

- Length of hospital stay (days) at 90 days
- Discharge destination (remains in hospital, home, care home) at 90 days
- Number of antibiotics doses received during first 7 days after randomisation
- Highest recorded CRP concentration (mg/L) during first 7 days after randomisation
- Highest recorded WBC count (x10⁹/l) during first 7 days after randomisation
- Highest recorded respiratory rate (RR)/minute during first 7 days after randomisation
- Highest recorded temperature °C during first 7 days after randomisation
- Highest recorded NEWS-2 score during first 7 days after randomisation
- Lowest recorded lowest oxygen saturations (%) during first 7 days after randomisation
- Caregiver quality of life (EQ-5D-5L)

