7.5 Baseline data

Baseline information will be collected from consented participants that meet all eligibility criteria. This includes but is not limited to:

- Baseline demographics:
 - Date of birth
 - Sex
 - Ethnicity
 - Pre-stroke mRS
 - Baseline EQ-5D-5L
- Time since symptom onset or last seen well to admission and randomisation
- Vascular risk factors:
 - Hypertension
 - Smoking history
 - Alcohol intake
 - Atrial fibrillation
 - Diabetes
 - Dyslipidaemia
 - Coronary artery disease
 - Peripheral vascular disease
 - Previous stroke
- Selected past medical history:
 - Chronic lung diseases
 - Cancer
 - Dementia
 - Medications at baseline
- Stroke subtype:
 - Acute ischaemic stroke
 - Intracerebral haemorrhage
- Baseline stroke severity at admission (NIHSS score)
- Thrombolysis and/or thrombectomy treatment
- Current nutritional status:
 - Nil by mouth
 - Normal diet and fluids
 - Modified diet and fluids
 - Nasogastric tube feeding
 - Peripheral parenteral nutrition
- Previous treated infection earlier in this admission and/or 6 weeks prior to enrolment

CLASP

- Highest recorded in the 72 hours preceding randomisation:
 - Plasma CRP concentration (mg/L)
 - White blood cell (WBC) count and neutrophil count
 - RR (/minute)
 - Temperature (°C)
 - NEWS-2 score
- Lowest oxygen saturations (%)
- Oxygen requirements
- Presence of unilateral or bilateral chest signs on examination
- Clinical chest X-ray (CXR) or other radiology findings
- Antibiotic treatment since admission including initial antibiotic treatment plan
- Health and social care resource use
- Caregiver quality of life (EQ-5D-5L)

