10.5 Adjusted analysis

All analyses will be adjusted for the minimisation variables, baseline age (<80 v \geq 80years), stroke severity (NIHSS score <12 v \geq 12) and trial centre. Given the large number of centres involved, mixed effects regression models will be used, with trial centre included as a random effect.

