10.10 Economic evaluation

Economic evaluation will be performed by the Manchester Centre for Health Economics, University of Manchester. It will compare the cost and outcomes of standard care with standard care plus clarithromycin in PSP from the NHS/Personal Social Services perspective, using established quality criteria [38,39]. The impact of caregiver health and cost burden will also be explored [40].

Within-trial Cost-effectiveness Analysis – Will compare the difference in total health and social care cost and health outcomes for standard care with standard care plus clarithromycin over the study follow-up period (90 days).

Healthcare resource use per participant will be measured at baseline and at day 90 using routine data collection and a purposely designed healthcare services utilisation form (developed with the PPIE Group). Individual-level costs will be created by combining measured resource use with published unit costs. Costs will comprise:

- Secondary care (days spent on stroke unit, rehabilitation wards, general medical wards, intensive care unit, readmissions, Accident & Emergency, outpatient visits)
- Primary care (GP practice visits and phone contacts with the GP practice personnel)
- Time in care homes.

We will collect downstream health and social care costs and informal caregiver costs using an adapted Client Service Resource Inventory (CSRI) [41], combined with an adapted version of the Costs of Family Caregiving in Palliative Care(COFAC tool [42]). The COFAC tool has been shown to be valid, acceptable to caregivers and feasible to administer. The COFAC questionnaire seeks to capture data from a broad societal perspective which includes family caregiver costs. Health outcomes will be expressed as quality-adjusted life-years (QALYs). The EQ 5D-5L questionnaire will be administered to patients (or a proxy score from their caregivers) at baseline and at Day 90, so that QALYs can be calculated for each participant, using the area under the curve method. Following the NICE Reference Case, EQ-5D-5L responses will be converted to EQ-5D-3L utility values [43]. We will collect EQ-5D for caregivers and generate QALYs in the same way.

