Generalised linear model regression will estimate the total cost and total QALYs per arm controlling for baseline cost, baseline health utility, and other relevant participant characteristics. Bootstrapping will be used to handle stochastic uncertainty. The incremental cost-effectiveness ratio (ICER) will be calculated if either strategy is not dominated. Missing data will be handled using multiple imputation. Sensitivity analyses will investigate the robustness of the estimated ICER to different analysis assumptions.

Model-based Cost-effectiveness Analysis – Will compare the difference in cost and health outcomes for standard care with standard care plus clarithromycin over a lifetime time horizon (discount rate: 3.5%). A de novo cohort-level Markov model with an embedded decision tree will be developed to simulate the natural history of PSP and the impact of the intervention, with input from patients and clinicians.

Systematic reviews of existing cost effectiveness models in PSP, HAP, CAP and stroke will inform model structure. The Markov model health states will take into account level of disability from stroke using mRS scores [44]. Patient characteristics, transition probabilities, resource use and utilities associated with the two regimens will be taken from the trial population. Transition probabilities, resource use and utilities associated with stroke disease progression will be obtained from published evidence.

A probabilistic base case analysis will account for all input parameter uncertainty simultaneously. We will report total and incremental cost and QALYs, and ICER (if relevant). A cost-effectiveness threshold of £20-30,000 per QALY gained will be used to determine cost-effectiveness. A cost-effectiveness acceptability curve will report the probability of cost effectiveness and incremental net monetary benefit will be derived. Deterministic one-way sensitivity analyses will identify key drivers of cost-effectiveness. Potential scenario analyses include:

- 1. Alternative mapping methods to estimate EQ-5D-3L utility values from mRS
- 2. Inclusion of carer utility
- 3. Inclusion of carer costs.

Subgroup analysis will include stroke type, interval since admission, and whether the patient had received thrombolysis or thrombectomy.

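### The resource-use model in 10.3.3 omits the baseline that the protocol collects and that its own economic analysis uses; adding it is free, for a gain in precision of unknown size

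*Protocol*

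**What the plan says.** Section 10.3.3 assigns models outcome by outcome. EQ-5D-5L at 90 days gets a "general linear model adjusted for the baseline EQ-5D-5L". Resource use sits in the preceding bullet with three other outcomes and has no baseline term: "Home time, stroke-related health status, health and social care resource use and caregiver burden will be analysed using general linear models".

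Section 10.5 sets the covariates common to everything: "All analyses will be adjusted for the minimisation variables, baseline age" group, NIHSS group and centre, with centre as a random effect. It mentions no outcome baselines.

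Baseline resource use does exist. Section 7.5 lists it among the baseline data, and section 10.10 says "Healthcare resource use per participant will be measured at baseline and at day 90 using routine data collection". The same section models total cost, which is built from that resource use, "controlling for baseline cost, baseline health utility, and other relevant participant characteristics".

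Other non-primary outcomes also have a pre-randomisation counterpart. Section 3.3.3 lists exploratory outcomes such as "Highest recorded CRP concentration (mg/L) during first 7 days after randomisation", with WBC, respiratory rate, temperature, NEWS-2, lowest saturation and caregiver EQ-5D-5L. Section 7.5 collects the first five of these markers as "Highest recorded in the 72 hours preceding randomisation" and lists lowest saturation and caregiver EQ-5D-5L alongside. Section 10 names no model for any of these.

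**The concern.** Section 10.3.3 names a baseline covariate for one outcome and not for its neighbour, so for resource use the model reads as a stated choice and not as detail left open. It also disagrees with section 10.10, which does use the baseline of the cost derived from the same data. A reader of the results could then see two treatment comparisons of closely related quantities, one adjusted for prior use and one not, with no reason given for the difference.

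What is at stake is efficiency. Minimisation balances only age group, NIHSS group and centre. Where a baseline predicts the outcome, leaving it out gives a wider interval than necessary and leaves chance imbalance in that baseline within the estimate. The comparison remains unbiased under randomisation, and its interval already reflects such imbalance.

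**Working it through.** **1. Which analyses use a baseline**

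| Outcome | Status | Baseline collected | Own-baseline term in the analysis |
|---|---|---|---|
| EQ-5D-5L, 90 days | Secondary | Yes (7.5) | Yes (10.3.3) |
| Resource use, 90 days | Secondary | Yes (7.5, 10.10) | None named (10.3.3) |
| Total cost, from resource use | Economic | Yes (10.10) | Yes (10.10) |
| 7-day CRP, WBC, respiratory rate, temperature, NEWS-2, saturation | Exploratory | Yes (7.5) | No model specified |
| Caregiver EQ-5D-5L | Exploratory | Yes (7.5) | No model specified in 10.3.3 |

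Only the resource-use row shows a model that is fixed without its baseline. Sections 10.3.3 and 10.10 differ on it.

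**2. The plan's own figure**

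The protocol gives no power or precision figure for resource use. Its one sample-size figure is for the mRS: 524 per group, 90% power, two-sided 5%, common OR 0.7, control distribution 2:8:8:5:20:20:37 (section 10.1). The proportional-odds formula, with p̄ the mean of the control and OR-shifted distributions, is

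N total = 12(1.960 + 1.282)² / [ln(0.7)² × (1 − Σp̄³)].

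It gives 524.2 per arm, and power of 0.900 at 524 per arm, so the stated figure reproduces. It does not depend on this point. Below, 524 per arm serves only as a reference size; the number with resource-use data may differ.

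**3. What a baseline covariate could gain**

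Adjusting for a baseline with correlation r to the outcome multiplies the residual variance by 1 − r², and the interval width by √(1 − r²). **The protocol does not give r; 0.1 to 0.7 is an assumption.**

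At 524 per arm, the difference detectable with 80% power without the covariate is (1.960 + 0.842) × √(2/524) = 0.173 SD. With the covariate it is 0.173 × √(1 − r²). Power at the original 0.173 SD becomes Φ(2.802/√(1 − r²) − 1.960).

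| Assumed r | 1 − r² | √(1 − r²) | Interval narrower by | Detectable difference (SD) | Power at 0.173 SD |
|---|---|---|---|---|---|
| 0.1 | 0.99 | 0.995 | 0.5% | 0.172 | 80.4% |
| 0.3 | 0.91 | 0.954 | 4.6% | 0.165 | 83.6% |
| 0.5 | 0.75 | 0.866 | 13.4% | 0.150 | 89.9% |
| 0.7 | 0.51 | 0.714 | 28.6% | 0.124 | 97.5% |

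**4. Limits of the table**

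- The models already contain age group, NIHSS group and centre. The relevant quantity is the correlation given those covariates, which may be smaller than the raw r.
- For resource use the low end is plausible. The 90-day measure covers the index admission and contacts after discharge (section 3.3.2). A baseline measure cannot cover the rest of that stay or what follows it, and the protocol does not define the baseline period.

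**The case against.** The strongest reply has four parts.

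**Resource use is collected mainly for the economic analysis.** Section 3.3.2 says so, and that analysis does control for baseline cost. This stands in part: a reader might infer that the protocol ignores baseline resource use altogether, and section 10.10 shows that it does not. The 10.3.3 model remains, however, as a separate stated analysis without the term.

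**Section 10.5 sets a minimum.** That "All analyses will be adjusted for the minimisation variables" does not forbid further covariates; EQ-5D-5L receives one on top. This stands. Adding baseline resource use is therefore compatible with 10.5 and contradicts nothing in it.

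**The 7-day markers and caregiver EQ-5D-5L are exploratory.** A reader might infer that CRP, NEWS-2 and the others are to be compared without their baselines. The protocol does not say that. Section 10.3.3 does not mention them, no model is fixed for them, and sections 10.3 and 10.9 leave the final analyses to a separate SAP. The protocol specifies no own-baseline adjustment for them and does not rule one out. Nor does it rank these markers as its main evidence on mechanism.

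**The gain may be negligible.** This also stands as a possibility: at r = 0.1 the interval narrows by 0.5%. It is tempting to express the gain as extra participants on the base of 1048, but that base is the mRS sample size and the result would rest wholly on an assumed r.

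**Conclusion.** The point holds for one secondary outcome. Section 10.3.3 fixes a resource-use model without a baseline that the trial collects, and section 10.10 treats the derived cost differently. For the exploratory 7-day markers and caregiver EQ-5D-5L there is no error in the protocol, only an opportunity to state a rule now.

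The gain is in precision and its size is unknown: about 0.5% to 28.6% off interval width for an assumed r of 0.1 to 0.7, possibly less after allowing for the covariates already present, and for resource use quite possibly near the low end. Validity, the primary mRS analysis and the sample size are unaffected. Severity is low; the case for acting is that the change needs no new data.

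**What to change.** 1. In section 10.3.3, add baseline resource use as a covariate in the resource-use model, in line with section 10.10, and state the period that the baseline measure covers.
2. In section 10.5 or the SAP, state that any non-primary outcome also measured before randomisation is adjusted for its own baseline value, as a continuous covariate, in addition to the minimisation variables. This covers 7-day highest CRP, WBC, respiratory rate, temperature and NEWS-2, lowest saturation, and caregiver EQ-5D-5L.
3. Add a simple rule for missing baselines, such as single imputation that uses neither outcome nor allocation. Section 10.8 makes complete-case data the basis of the main analyses, so without a rule a missing baseline would drop the participant. The pre-randomisation markers are whatever was recorded beforehand, and the protocol gives no missingness rate.

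The cost is a few sentences of wording. No new data, visits or participants are needed.
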